**Data Analyses**

**Power and Sample Size Justification:**

For the past 9 months, members of the study team have collected data comparing the effect of wearing the MyoPro Motion G versus not wearing the MyoPro Motion G on UE movement in moderately impaired stroke survivors. This work showed a mean change of 8.72 ± 7.1 points on the UE FM when subjects wore the MyoPro Motion G (Table 3). From this work, we have formed the primary study hypothesis, which is that subjects will exhibit significantly higher scores on the UE FM when using the MyoPro 2 Motion G compared to scores when using the splint and no device.

**Table 3:** Pilot Data Leading to the Current Trial

condition	Method	Mean	99% CL Mean		Std Dev	99% CL Std Dev		99% UMPU CL Std Dev	
with		27.2778	21.9152	32.6403	7.8501	5.4157	13.5603	5.3232	13.2488
without		18.5556	14.2528	22.8583	6.2987	4.3454	10.8803	4.2712	10.6304
Diff (1-2)	Pooled	8.7222	2.2498	15.1947	7.1168	5.4042	10.2156	5.3562	10.1038
Diff (1-2)	Satterthwaite	8.7222	2.2318	15.2127					

Method	Variances	DF	t Value	Pr >  t
Pooled	Equal	34	3.68	0.0008
Satterthwaite	Unequal	32.475	3.68	0.0008

[figure not shown]
Equality of Variances				
Method	Num DF	Den DF	F Value	Pr > F
Folded F	17	17	1.55	0.3729

Based on the above work, we have taken a very conservative estimate of effect size (Table 4), and estimate that a sample size of  $n=49$ , will provide approximately 80% power to detect a medium effect size of  $f=0.2521$  when alpha is set to 0.05 for repeated measures MANOVA with 1 group and 3 measurements, using the  $F$ -distribution. (Figure 2). Given a liberal attrition rate of 20% and the need to examine age-associated differences in depth (i.e., covariates such as age and time since stroke), we plan to enroll up to a total of 75 participants ( $n = 75$ ) to ensure adequate power for the planned analyses.

**Table 4:** Point Estimate and 95% Confidence Interval Effect Size,  $d$  and  $f$

	Effect Size		
	Point Estimate	95% Lower Bound	95% Upper Bound
$d$	1.22667	0.50413	1.93409
$f$	0.6134	0.2521	0.9670

**Figure 2:** Differences Between Independent Means and Power/Sample Size Estimates

"Functional Assistance provided by Myoelectric Elbow-wrist-hand orthoses" (FAME)

Desired Power	Required Sample Size
0.600000	32.393509
0.610000	33.035972
0.620000	33.689708
0.630000	34.355391
0.640000	35.033746
0.650000	35.725556
0.660000	36.431665
0.670000	37.152989
0.680000	37.890523
0.690000	38.645352
0.700000	39.418662
0.710000	40.211754
0.720000	41.026061
0.730000	41.863165
0.740000	42.724820
0.750000	43.612981
0.760000	44.529834
0.770000	45.477833
0.780000	46.459755
0.790000	47.478749
0.800000	48.538415
0.810000	49.642895
0.820000	50.796985
0.830000	52.006284
0.840000	53.277389
0.850000	54.618146
0.860000	56.037995
0.870000	57.548430
0.880000	59.163657
0.890000	60.901520
0.900000	62.784876
0.910000	64.843687
0.920000	67.118332
0.930000	69.665121
0.940000	72.566040
0.950000	75.947367

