MyoPro has an immediate, discernible impact on UE movement and functional limitation, especially for patients who may be prescribed such a device with limited opportunities to participate in multi-week UE therapy regimens. In pilot work leading to the current study, we showed clinically-important increases in UE movement when wearing the MyoPro Motion G (+8.2 points on the upper extremity Fugl-Meyer scale; a widely used, stroke-specific measure) as well as reduced functional limitation and increased gross manual dexterity immediately after 18 subjects with chronic, stable, moderate UE impairments donned the MyoPro Motion G. As a next step, the primary study objective is to compare UE movement while wearing the MyoPro 2 Motion G versus a resting splint and no device in stroke survivors with moderate UE dysfunction. During the study, subjects will undergo general training in the operation of the EMG-controlled orthosis and the comparison orthosis, and then guided through a series of standard clinical outcome measures. These outcome measures will allow the researchers to directly compare the relative benefit of the MyoPro 2 Motion G with a resting hand splint and no device in reducing UE impairment and increasing UE dexterity and functional task performance.

**Specific Aim 1: Determine the impact of the MyoPro 2 Motion G myoelectric brace on affected UE movement.** 75 stroke survivors exhibiting moderate UE impairment will be administered the UE FM while wearing: (a) the MyoPro 2 Motion-G (b) a comparison resting hand splint, and (c) no device, with the order of assessment conditions randomized and counterbalanced across subjects. This study design will allow investigators to determine the immediate impact of the MyoPro 2 Motion G on increasing UE movement when compared to a commonly-prescribed device (resting hand splint) and compared to no device

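### The paired pilot is analysed as two independent groups, so the ± 7.1 is not the SD of change and the f that sets n=49 is a two-sample limit

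*Protocol*

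**What the plan says.** The Specific Aims section describes pilot gains seen "immediately after 18 subjects with chronic, stable, moderate UE impairments donned the MyoPro Motion G". The Power and Sample Size Justification describes the same work as "comparing the effect of wearing the MyoPro Motion G versus not wearing the MyoPro Motion G on UE movement" and summarises it thus: "This work showed a mean change of 8.72 ± 7.1 points on the UE FM".

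Table 3 gives a mean of 27.2778 (SD 7.8501) with the device and 18.5556 (SD 6.2987) without it. The difference is 8.7222, shown in a Pooled row with SD 7.1168 and in a Satterthwaite row. The tests are t=3.68 on 34 df and a folded F on 17 and 17 df. Table 4 gives d=1.22667 (95% limits 0.50413 and 1.93409) and f=0.6134 (0.2521 and 0.9670).

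The text then says "we have taken a very conservative estimate of effect size (Table 4") and that n=49 "will provide approximately 80% power to detect a medium effect size of" f=0.2521, at alpha 0.05, for a repeated measures MANOVA with one group and three measurements. The power table is titled "Differences Between Independent Means and Power/Sample Size Estimates". With 20% attrition and covariates in mind, enrolment is set at up to 75.

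**The concern.** Eighteen people with 18 scores in each condition make 18 pairs. A paired analysis has 17 df and rests on the SD of the within-person differences. Table 3 has 34 df, pooled and Satterthwaite rows and an equality-of-variances test, which is output for two separate groups.

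Two figures in the sample size justification inherit this. The first is the SD attached to the mean change in the primary outcome, which a reader would take as the SD of change and might reuse as such. The second is the lower limit of the effect size. Its sampling error depends on the pairing, and it is the value from which n=49 is obtained. Without the with/without correlation, the protocol does not show whether its cautious planning value is more or less cautious than the pilot supports.

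**Working it through.** **Inputs.** From Table 3: SDs 7.8501 and 6.2987, difference 8.7222, 18 scores per condition, t=3.68. From the text: alpha 0.05, three measurements, n=49, enrolment 75, attrition 20%. Not given: the pilot correlation r between scores with and without the device, and the correlation rho among the repeated measures in the power calculation. Both are assumptions below.

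**1. Reproduce Table 3 as a two-sample analysis.**
- Pooled SD = sqrt((7.8501² + 6.2987²)/2) = 7.1168. This is the ± 7.1.
- t = 8.7222 / (7.1168 × sqrt(2/18)) = 3.677 on 18 + 18 − 2 = 34 df.
- The 99% interval is 2.25 to 15.19, as printed.

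**2. Reproduce Table 4.**
- d = 3.68 × sqrt(2/18) = 1.22667.
- Inverting the noncentral t on 34 df gives 95% limits 0.50413 and 1.93409, as printed.
- Half the lower limit is 0.2521.

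**3. Reproduce the power table.** Take a noncentral F on 2 and N−2 df with noncentrality 3·N·f²/(1−rho) and f=0.2521. Setting rho=0.1 gives N = 32.3935, 39.4187, 48.5384, 62.7849 and 75.9474 at 60, 70, 80, 90 and 95% power, all matching the protocol. Power at 49 is 80.4%. With rho=0, N would be 53.6; with rho=0.5, 28.4. So n=49 follows from f=0.2521, but only with a correlation of 0.1 that the protocol does not state. The formula is for repeated measures, so the independent-means title on the table is a mislabel.

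**4. SD of change.** SDdiff = sqrt(7.8501² + 6.2987² − 2·r·7.8501·6.2987). This equals 7.1168 only at r = 0.51.

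**5. Paired lower limit.** Take t = 8.7222/(SDdiff/sqrt(18)) and find the lower 95% noncentrality on 17 df. Divide by sqrt(18), then multiply by SDdiff/7.1168 to return to the protocol's scale. This gives d; f=d/2, as in Table 4. The rescaling treats the ratio of SDs as known, so the limit is approximate.

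**6. Sample size and power**, with the formula in step 3 and rho set equal to r:

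| r | SD of change | lower d | lower f | n for 80% | power at 49 | power at 60 | power at 75 |
|---|---|---|---|---|---|---|---|
| 0 | 10.06 | 0.442 | 0.221 | 69 | 63.7% | 73.7% | 83.7% |
| 0.1 | 9.56 | 0.470 | 0.235 | 56 | 74.3% | 83.4% | 91.3% |
| 0.5 | 7.20 | 0.594 | 0.297 | 22 | 99.6% | 99.9% | >99.9% |
| 0.8 | 4.71 | 0.709 | 0.354 | 9 | >99.9% | >99.9% | >99.9% |

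The column for 60 is 75 less 20% attrition. Power at 49 reaches 80% at r = 0.16. The paired f passes 0.2521 at r of about 0.22.

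**7. Sensitivity to the conversion from d to f.** f=d/2 is the two-group conversion. If the device sits d above two equal comparators (an assumption), f = (sqrt(2)/3)·d = 0.471d. Then n for 80% power is 78, 62, 24 and 10 in the four rows, and n=49 reaches 80% at r of about 0.20.

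**The case against.** Four points can be made for the plan.

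- **Scale.** Dividing by the pooled within-condition SD is acceptable for f when the correlation enters the formula separately, as it does here. This stands. The point estimate d=1.22667 on that scale does not depend on the pairing. What does depend on it is the confidence limit and the label on the ± 7.1.
- **Little turns on the exact limit.** The power statement is conditional on f. A round f=0.25 with rho=0.1 would give N=49.3, almost the same as 48.5. Even the lowest paired limit, 0.221, is far below the pilot estimate of 0.6134. This also stands, and it is why the point does not threaten the enrolment figure. But the protocol presents 0.2521 as the pilot's 95% lower limit, and for a paired pilot it is not.
- **Harm needs a low correlation.** The same scale was scored in the same people with stable impairment, so r near zero is the least natural assumption. With 60 completers, 80% power at the paired limit is reached once r exceeds about 0.06 under f=d/2. That is fair, yet the protocol's own power table rests on a correlation of 0.1, and at that value n=49 falls short at the paired limit.
- **The table above stacks assumptions.** It sets rho equal to r. If rho is held at 0.1 whatever r is, n for 80% runs only from 63 at r=0 to 27 at r=0.8. The range is narrower and its direction is the same.

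The source of the 7.1 can be traced, since the Table 3 row is marked Pooled. That does not make it the SD of a change, which is what the sentence calls it.

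**Conclusion.** The concern holds. The ± 7.1 is the pooled SD of scores, not the SD of change. The f=0.2521 behind n=49 is half a two-sample lower limit on 34 df, applied to 18 pairs. Both follow from exact reproduction of Tables 3 and 4 and need no assumption beyond the pairing that the protocol itself describes.

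The size of the error rests on the unreported r. Over r = 0 to 0.8, the true SD of change could be from about 3 points above the stated 7.1 to about 2.4 points below it, and the paired f from 0.221 to 0.354. At r below about 0.16 (about 0.20 with f=0.471d), n=49 has less than 80% power at the paired limit; above that it is conservative.

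The consequence is limited. With f=d/2 and rho=r, all 75 participants give about 84% power or more across the range. Sixty completers give 74% at r=0 and 83% at r=0.1. Nothing here shows that 75 is too few. The section should still be corrected, because it states wrong figures for the primary outcome.

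**What to change.** Re-analyse the 18 pilot pairs with a paired test. In the Power and Sample Size Justification:

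1. Replace the 8.72 ± 7.1 with the mean and SD of the paired differences, and replace the two-sample output in Table 3.
2. Report the with/without correlation and the paired 95% interval.
3. Restate the lower-limit f, the n for 80% power and the power at the planned size, with one stated correlation used throughout. Say how d is converted to f for three conditions.
4. Retitle the power table so that it does not refer to independent means.
5. As an editorial matter, reconcile the gain of "8.2 points on the upper extremity Fugl-Meyer scale" in the Specific Aims with the 8.72 given here. The 8.2 enters no calculation.

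The cost is a short re-analysis of data the sponsor already holds and rewording within one section, plus the single figure in the Specific Aims. Enrolment does not change.

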### **Comparison Device**

The Comfy Dorsal Hand Splint (Comfy Splints, Lenjoy Medical Engineering, Inc.) (Figure 2) was chosen for the comparison device, as splints are among the most commonly-prescribed products post-stroke and are used to place the affected arm in a functional position and prevent deformity. The dorsal splint was chosen (as opposed to a palmar splint) as it leaves the digits free for object manipulation and task performance.

**Figure 2:** Comfy Dorsal Hand resting splint

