**Secondary Study Hypotheses:**

**Hypothesis 2a:** Subjects will exhibit significantly higher scores on the B&B when using the MyoPro 2 Motion G compared to scores when using the splint and no device.

**Hypothesis 2b:** Subjects will exhibit significantly higher quality scores and decreased time on the battery of functional tasks when using the MyoPro 2 Motion G compared to scores when using the splint and no device.

We will evaluate primary and secondary study hypotheses using repeated measures MANOVA. The independent variable is device usage and has three levels: (1) performance with MyoPro 2 Motion G, (2) performance with the resting hand splint, and (3) performance without device. The multiple dependent variables include: (1) UE movement as measured by the UEFM (primary hypothesis), (2) dexterity as measured by the B&B (hypothesis 2a), and (3) functional movement as measured by the novel battery (hypothesis 2b). A significant main effect and/ or interaction effect will be investigated in greater detail using univariate tests. These analyses are powered to permit inclusion of 1-2 covariates such as participant age and time since stroke. Post-hoc analyses will include a specific contrast for participants aged 65 and over.

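### The planning effect f=0.2521 is a two-condition conversion of the pilot d, used for three conditions with no stated pattern of means or correlation

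*Protocol*

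**What the plan says.** In the Protocol, Power and Sample Size Justification, the pilot is described as "comparing the effect of wearing the MyoPro Motion G versus not wearing the MyoPro Motion G on UE movement", which is two conditions. Table 3 gives a mean difference of 8.7222 Fugl-Meyer points and a pooled SD of 7.1168. Table 4 lists d and f side by side: 1.22667 and 0.6134 (point estimate), 0.50413 and 0.2521 (95% lower bound), 1.93409 and 0.9670 (95% upper bound).

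The section states "we have taken a very conservative estimate of effect size (Table 4"). The lower-bound f is then used "when alpha is set to 0.05 for repeated measures MANOVA with 1 group and 3 measurements", giving n=49 for about 80% power. A printed table gives the required n for powers from 0.60 to 0.95, with 48.538415 at 0.80. Enrolment is set at up to 75: "Given a liberal attrition rate of 20% and the need to examine age-associated differences in depth".

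The analysis text under Secondary Study Hypotheses confirms the design: "The independent variable is device usage and has three levels", namely MyoPro, splint and no device. The sample-size section gives no expected splint mean and no correlation among the three measurements.

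**The concern.** Cohen's f is the SD of the condition means divided by the common SD. With two means a distance d apart, f is exactly d/2. With three means it depends on where the third one lies, and the protocol does not say. The number labelled as the pilot's lower bound is therefore not, in general, the f of a three-condition trial whose MyoPro versus no-device difference sits at that bound.

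n=49 and the description of the effect as very conservative both rest on this number. If the true three-condition f is smaller, the n for 80% power at the pilot bound is larger than 49. Some of the room between 49 and 75 is then already spent, although the plan also relies on that room for attrition and covariates ("These analyses are powered to permit inclusion of 1-2 covariates such as participant age and time since stroke").

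**Working it through.** **Inputs.** From the protocol: d=0.50413 and f=0.2521 (Table 4), pooled SD 7.1168 (Table 3), alpha 0.05, three measurements, n=49, attrition 20%, enrolment 75. Not in the protocol: the within-subject correlation rho and the splint mean.

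**1. How Table 4 gets f.** 0.50413/2 = 0.25207, 1.22667/2 = 0.61334 and 1.93409/2 = 0.96705. These match the printed f values to within rounding in the last digit. Every f is d/2.

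**2. Reproducing the plan's n.** For a one-group repeated measures MANOVA with three measurements, I use a noncentral F with df 2 and N−2 and lambda = 3Nf²/(1−rho). With f=0.2521 and rho=0.1 this returns N = 32.393509, 39.418662, 48.538415, 62.784876 and 75.947367 for power 0.60, 0.70, 0.80, 0.90 and 0.95. All 36 printed rows match. Power at n=49 is 80.4%. At rho=0 the n would be 53.6, and at rho=0.25 it would be 41.0, so the table was built with rho=0.1.

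**3. f for three conditions at the pilot bound.** Put no device at 0, MyoPro at d and the splint at −xd. The population variance of the three means is d²(2+2x+2x²)/9.

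- Splint equal to no device (x=0): f = d√2/3 = 0.50413 × 0.4714 = 0.2376.
- For f = d/2: (2+2x+2x²)/9 = 1/4, so x² + x − 0.125 = 0 and x = 0.112. The splint must lie 0.112 × 0.50413 × 7.1168 = 0.40 points below no device. By symmetry, 0.40 points above MyoPro gives the same f.

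**4. Power with only that link changed** (splint equal to no device, rho=0.1):

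| | f | Power at 49 | N for 80% | Enrolment at 20% attrition | Power at 60 |
|---|---|---|---|---|---|
| As planned | 0.2521 | 80.4% | 49 | 49/0.8 = 61.25, so 62 | 88.5% |
| Three-condition f | 0.2376 | 75.3% | 54.23, so 55 | 55/0.8 = 68.75, so 69 | 84.3% |

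The 60 is 75 × 0.8. Both enrolment figures lie within 75.

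**5. Sensitivity to the two unstated inputs.**

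- Correlation, with f=0.2376: power at n=49 is 70.5% at rho=0, reaches 80% at rho of about 0.19, and is 95.2% at rho=0.5. At 60 completers it is 80.1% at rho=0 and rises from there.
- Splint mean, at rho=0.1: 0.40 points below no device restores f=0.2521. One point below gives f=0.277 and 87.5% at n=49.

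**6. What f=0.2521 means with the splint equal to no device.** d = 0.2521 × 3/√2 = 0.535 SD, and 0.535 × 7.1168 = 3.81 points. The pilot lower bound is 0.50413 × 7.1168 = 3.59 points.

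**The case against.** The best reply is that nothing printed is false in isolation. Table 4 converts a two-condition pilot correctly, and n=49 does give about 80% power for f=0.2521. Both statements stand. What does not stand is the link between them, because the text takes f from the pilot bound and uses it for three conditions without saying what the third mean is.

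The second reply is that the direction of the discrepancy is not fixed by the documents. That is right. The Comparison Device section says only that splints "are used to place the affected arm in a functional position and prevent deformity" and that the dorsal type leaves the fingers free. It does not indicate whether a splinted arm scores above, at or below an unaided one. A splint slightly below no device would make f=0.2521 accurate or even low. A slightly higher correlation than the inferred 0.1 would also close the gap.

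A reader might go the other way and infer that the trial is underpowered. The tempting figures come from a splint midway between the other conditions: f = d/√6 = 0.206, power 62% at n=49 and 72% at 60 completers, and N=72 for 80%. The documents do not suggest that pattern, and even there 60 completers reach 80% once the correlation is about 0.25. The planning effect also remains below half of the observed 8.72 points, so calling it conservative relative to the pilot estimate is fair.

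**Conclusion.** The point holds as a minor one about where a planning figure comes from. f=0.2521 is not the three-condition equivalent of the pilot's lower bound unless the splint lies about 0.4 points below no device or as far above MyoPro, and the protocol assumes neither. With the splint equal to no device and rho=0.1, power at n=49 at that bound is 75% rather than 80%, and 80% needs 55 completers rather than 49. This size rests on an assumed splint mean and a back-solved correlation. The algebra that d/2 is a two-mean relation does not depend on either.

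It should not be read as an error in the step from f to n, nor as evidence that 75 is too few. With the splint equal to no device, 60 completers give 84% at rho=0.1 and at least 80% for any correlation of 0 or above.

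**What to change.** Either of two edits to Power and Sample Size Justification is enough.

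- State the three assumed condition means, the SD and the correlation, and derive f from them. For example: at the 95% lower bound of the pilot effect (d=0.504), with equal means for splint and no device, f=0.238; with a within-subject correlation of 0.1 and alpha 0.05, 55 completers give 80% power and 60 give 84%. The printed power table would be recalculated to match.
- Or keep f=0.2521 and n=49, state the correlation of 0.1 if the sponsor confirms it, and say that this f corresponds to a 3.81-point MyoPro advantage with the splint equal to no device, not to the pilot lower bound of 3.59 points.

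The cost is about two sentences and, for the first option, one recalculated table. Enrolment stays at 75, and conduct and analysis are unchanged. The only drawback is a slightly less favourable stated figure.

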**Data Analyses:**

**Primary Study Hypothesis:** Subjects will exhibit significantly higher scores on the UE FM when using the MyoPro 2 Motion G compared to scores when using the splint and no device.

**Secondary Study Hypotheses:**

**Hypothesis 2a:** Subjects will exhibit significantly higher scores on the B&B when using the MyoPro 2 Motion G compared to scores when using the splint and no device.

**Hypothesis 2b:** Subjects will exhibit significantly higher quality scores and decreased time on the battery of functional tasks when using the MyoPro 2 Motion G compared to scores when using the splint and no device.

We will evaluate primary and secondary study hypotheses using repeated measures MANOVA. The independent variable is device usage and has three levels: (1) performance with MyoPro 2 Motion G, (2) performance with the resting hand splint, and (3) performance without device. The multiple dependent variables include: (1) UE movement as measured by the UEFM (primary hypothesis), (2) dexterity as measured by the B&B (hypothesis 2a), and (3) functional movement as measured by the novel battery (hypothesis 2b). A significant main effect and/ or interaction effect will be investigated in greater detail using univariate tests. These analyses are powered to permit inclusion of 1-2 covariates such as participant age and time since stroke. Post-hoc analyses will include a specific contrast for participants aged 65 and over.

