## **Data Collection Procedures**

### **Study Protocol Overview:**

All subjects will be requested to participate in 4 study visits lasting no more than 3 hours each, as well as three training sessions of approximately 1 hour each (Table 2). During the first study visit, the study will be explained to the subject and written informed consent will be obtained. Then, all screening measures (listed in Table 1) will be administered and, if the subject meets all inclusion criteria, they will move on to the educational sessions. Between visits #1 and #2, the subjects will receive two education sessions, (1 one-hour training session and 1 two-hour training session) on both the MyoPro 2 Motion G and comparison splint. During study visits #2, #3 & #4, the subject will undergo all outcome measures (Table 1) in all three conditions (one condition per visit to minimize fatigue) in randomized order. A summary of the study timeline and a more detailed description of the study design follows.

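### Repeated measures MANOVA in its standard form discards partial completers; a likelihood-based mixed model for UE FM alone would use every observed visit and needs a weaker assumption about dropout

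*Protocol*

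**What the plan says.** The analysis paragraph under Secondary Study Hypotheses fixes one method for all hypotheses: "We will evaluate primary and secondary study hypotheses using repeated measures MANOVA". Device condition is the within-subject factor, with three levels. The outcomes enter together: "The multiple dependent variables include: (1) UE movement as measured by the UEFM (primary hypothesis"), then B&B and the functional battery. Significant effects are followed up with univariate tests.

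The Study Protocol Overview places all outcomes for one condition at a single visit ("one condition per visit to minimize fatigue"), using Visits 2, 3 and 4. Description of Study Visits adds that a Latin square counterbalances the order.

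Power and Sample Size Justification sizes the trial "when alpha is set to 0.05 for repeated measures MANOVA with 1 group and 3 measurements". It says that 49 subjects "will provide approximately 80% power to detect a medium effect size of" f = 0.2521. The attrition allowance reads "Given a liberal attrition rate of 20" per cent, and "we plan to enroll up to a total of 75 participants".

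**The concern.** One condition per visit means that a subject who leaves early has UE FM for one or two of the three conditions. Standard repeated measures MANOVA needs a complete vector for each subject, so it deletes that subject, including the scores already collected. If the three outcomes are analysed jointly, a missing B&B or battery value removes a complete set of UE FM scores from the primary test as well. With 20% attrition allowed for, partial completers are foreseeable.

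Two things could be at stake. One is precision. The other is validity: deleting partial completers is generally safe only if dropout is unrelated to outcome. A subject can leave after a session that went badly. With counterbalanced order, about two-thirds of subjects meet the MyoPro at their first or second assessment and could leave after it.

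**Working it through.** **1. The protocol's sample size.** Inputs from Power and Sample Size Justification: f = 0.2521, alpha 0.05, 1 group, m = 3 measurements. For a one-group within-subject MANOVA, the F test has 2 and N − 2 degrees of freedom and noncentrality λ = N·f²·m/(1 − ρ). With ρ = 0.1, 80% power needs N = 48.538, which is the protocol's tabulated value (48.538415, rounded to 49). The protocol does not state ρ; 0.1 is the value its table implies.

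**2. Does enrolment cover attrition?**
- Needed with 20% attrition: 49/0.8 = 61.25, so 62.
- Completers from 75: 75 × 0.8 = 60, which is 11 more than 49.
- Power at 60, interpolated between the table's 0.88 (n = 59.16) and 0.89 (n = 60.90): about 0.885.
- Loss that still leaves 49: 26/75 = 34.7%.

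**3. Precision lost through the method itself.** Having 60 complete subjects instead of 75 raises the standard error (SE) by √(75/60) = 1.118, about 12%. Most of this is unavoidable. Simulations of 75 subjects with about 60 complete and random dropout compared complete cases with a likelihood fit to all observed data, for MyoPro minus no device:

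| Setting | Complete case against likelihood |
|---|---|
| SD 7.1, ρ 0.1 / 0.5 / 0.7, all dropout after the first or second assessment | variance ratio 1.12 / 1.09 / 1.10, so SE ratio 1.06 / 1.04 / 1.05 |
| Same design, repeated independently | variance 8-14% larger, so SE about 4-7% larger |
| Pilot means and SDs (Table 3), ρ 0.5 / 0.8, one third of dropouts lost before Visit 2 | SE 0.983 v 0.950 / 0.628 v 0.611, about 3% larger |

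The cost of MANOVA itself is therefore about 3-7% of the SE. It is nil for subjects lost before Visit 2, who give no condition-specific data to any model.

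**4. Bias on UE FM (points, MyoPro minus no device).** Random dropout gives no bias with either method. Under assumed dropout mechanisms:

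| Assumed mechanism | Complete case | Likelihood |
|---|---|---|
| Leaves after a low MyoPro score (60% v 15%), ρ 0.1 / 0.5 / 0.7 | +0.86 / +0.47 / +0.22 | 0.00 / −0.03 / −0.07 |
| Same, repeated independently (low = bottom third) | +0.90 / +0.50 / +0.31 | 0.05 or less |
| Always leaves after a MyoPro score in the lowest 30%, ρ 0.5 / 0.8 | +1.31 / +0.77 | −0.04 / −0.03 |
| Skips the MyoPro visit and all later ones, expecting little benefit, ρ 0.5 / 0.8 | +2.23 / +1.50 | +2.19 / +1.50 |

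In the first three rows dropout depends on an observed score, and the likelihood fit removes the bias. In the last row it depends on something never observed, and neither method copes.

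**5. Bound in either direction.** If the 20% lost were exactly those with the smallest (or largest) paired difference, the bias would be 0.35 × the SD of that difference. The factor is the standard normal density at the 20th percentile divided by 0.8. From the Table 3 SDs at ρ = 0.5, the SD is √(7.85² + 6.30² − 2 × 0.5 × 7.85 × 6.30) = 7.20, giving ±2.5 points. At ρ = 0.8 the SD is 4.71, giving ±1.6 points.

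**The case against.** **The protocol never says complete cases only.** Handling of missing data may sit in the SAP, which is not shown, and imputation followed by MANOVA would fit the text. This stands as far as silence on missing data goes, and that silence is not the point here. The protocol does fix a named method, and that method in its standard form deletes partial completers.

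**Precision is already covered.** A reader might infer that 20% attrition leaves the trial short of information. It does not: 60 completers exceed 49. Recovering 9-12% of the variance would be worth about 5-7 subjects and would move power from about 0.885 to about 0.91-0.92 on the protocol's table.

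**Bias towards the MyoPro is not shown.** A reader might infer that the result will flatter the MyoPro. Nothing in the protocol says who leaves or why. The dropout rates above are assumed, and the bias reverses if subjects who do poorly without the device are the ones who leave.

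**Joint deletion across outcomes is one reading.** The power calculation reproduces with a single outcome over three conditions, and univariate follow-up tests are planned. Those tests, run outcome by outcome, would avoid deletion for a missing secondary value, but not deletion for a missed condition. Nor do the documents support a large loss from scattered missing values. An assumed 2% per outcome-by-condition cell, independent over 9 cells, gives 1 − 0.98⁹ = 16.6%. The same 2% clustered by visit gives 1 − 0.98³ = 5.9%. Inability is also largely scorable, since the battery has a zero score and B&B is a count.

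**Conclusion.** The point holds as a matter of method, at modest size. The named MANOVA, in standard form, drops partial completers whom the design makes foreseeable, and it is generally valid only if dropout is unrelated to outcome. A likelihood-based model is valid under the weaker missing-at-random assumption and is slightly more precise.

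Under an assumed pattern of leaving after a low MyoPro score, the complete-case bias is roughly +0.2 to +1.3 points, or 2.5% to 15% of the 8.72-point pilot difference (0.22/8.72 and 1.31/8.72). That would distort the estimate but is unlikely to reverse a conclusion of the pilot's size.

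These figures assume normal scores, no period effect, about 20% loss and within-subject correlations of 0.1 to 0.8. The protocol gives no paired SD or correlation: the 7.1 in "This work showed a mean change of 8.72 ± 7.1 points on the UE FM" is the pooled SD in Table 3, not the SD of paired differences. The simulation using the pilot values also takes the splint as equal to no device.

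**What to change.** In the analysis paragraph under Secondary Study Hypotheses, replace the MANOVA for the primary hypothesis with a likelihood-based repeated-measures mixed model for UE FM alone, using all observed visits. Include condition and period as fixed effects. Period matters here because dropout removes later visits, so the observed data no longer have conditions balanced over visits. Test MyoPro against splint and MyoPro against no device as contrasts in that model. Analyse B&B and the battery in separate models of the same kind, so that a missing secondary value cannot remove primary data. Keep the complete-case analysis as a sensitivity analysis.

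The cost is analysis wording and slightly more specification; no further subjects, visits or data are needed. The model still assumes missing at random, so it does not protect against subjects who skip the MyoPro visit for unobserved reasons.
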